#### 4.4.2 Dose Delays

Participants who experience toxicity should have study drug held pending assessment, management, and resolution of the toxicity. Participants in whom the toxicity is assessed to be unrelated to study drug or for whom the toxicity does not meet the criteria for discontinuation, may reinstitute study drug as per guidelines outlined in [Section 4.4.1](#) and [Section 7](#). Reinstitution of study drug shall be conducted as follows:

- For participants in whom the toxicity is assessed to be related to study drug, dose delays of up to 21 days are allowed.
- For participants in whom the toxicity is unrelated to study drug, dose delays of up to 21 days are allowed. Dose delays up to 4 weeks are allowed for participants who require palliative radiotherapy only in consultation with the medical monitor (see [Section 8.1.1](#)).

- The medical monitor must be consulted prior to the restart of study drug after a dose delay.

A participant with a dose delay > 21 days due to an AE, but who has otherwise experienced clinical benefit, in the judgement of the investigator in consultation with medical monitor, may continue to receive study drug.

#### **4.4.2.1 COVID-19/SARS-CoV-2 Infection or Vaccination**

The following guidelines apply to participants with confirmed (positive by regulatory authority approved/authorized test) or presumed (test pending/clinical suspicion) coronavirus disease 2019 (COVID-19)/severe acute respiratory syndrome coronavirus 2 (SARS-CoV-2) infection:

- For participants with confirmed or presumed SARS-CoV-2 infection, study drug should be delayed for at least 14 days from the start of symptoms. Consideration for study treatment continuation will be made on a case-by-case basis with the medical monitor and the principal investigator.
- Prior to restarting study drug, participants should be afebrile for at least 72 hours and SARS-CoV-2-related symptoms should have recovered to  $\leq$  Grade 1 or baseline for a minimum of 72 hours.
- The sponsor should be informed when resuming study drug.

The sponsor must be informed within 24 hours of awareness of a participant with confirmed or presumed COVID-19/ SARS-CoV-2 infection. Suspected cases of COVID-19/ SARS-CoV-2 should be tested per local practice/institutional guidelines with an approved/authorized test.

At the discretion of the investigator, non-live COVID-19 vaccines may be administered per local practice. Participants may have study drug held to allow for COVID-19 vaccination; delays of up to 5 days are allowed.

#### **4.5 Study Duration**

It is expected that enrollment of the Dose Escalation Phase of the study (including Module A and Module B) will occur over approximately 18 months and that enrollment of the cohort expansion portions of the study will take approximately 12 months from the time of initiation of the Cohort Expansion Phase for each Module A and Module B.

The total time for conduct of the trial is expected to be approximately 78 months (which includes 2 years of survival follow-up). These estimates of the timing for study conduct may vary from that observed in the actual conduct of the trial.

## 4.5.1 Participant Accrual

The maximum number of participants to be enrolled in this study will be approximately 182 participants. This number of participants does not take into account participants who may be replaced or the possibility of expanding the mCRPC cohort with an additional 24 participants at the discretion of the sponsor.

The number of participants enrolled in the Dose Escalation Phase cannot be precisely determined in advance and could range from 6 up to 54 participants depending on results in the course of the trial and the number of dose levels explored. This participant number does not take into account replacement of non-evaluable participants or the possibility of expanding an individual escalation cohort up to 15 participants to allow for further evaluation of safety, PK, and antitumor activity of the study drugs at the dose level in that cohort.

The Cohort Expansion Phase of the study will enroll up to 128 participants. Module A Cohort Expansion Phase will enroll up to 16 participants into each of 5 cohorts (mCRPC, NSCLC, TNBC, SCCHN, and melanoma) treated with MGC018 monotherapy. Module B will enroll up to 16 participants into each of 3 cohorts treated with the combination of MGC018 and MGA012: participants with unresectable, locally advanced or metastatic SCCHN, mCRPC, and participants with a tumor type TBD at a later date. During the Cohort Expansion Phase of the study, participants who withdraw before completing the first tumor assessment for a reason other than progression of disease may be considered unevaluable for response. In these cases, additional participants may be enrolled. In addition, up to 4 participants may be added per cohort.

## 4.5.2 Definition of End of Study

The end of study will occur after the last participant has met off-study criteria and the data collection process is completed (time of study database lock).

End of study for each participant is defined as follows: participant is lost to follow-up (LTFU) ([Section 5.3](#)) or discontinues from the study due to any reason listed in [Section 5.5](#). Each participant's end of study status will be recorded in the End of Study CRF page.

## 4.6 Appropriateness of Measurements

Routine laboratory evaluations including hematology, chemistry, coagulation, endocrine tumor markers, and urinalysis will be carried out in local institutional laboratories. Additional local safety laboratory assessments may be used to supplement the protocol-prescribed assessments and may be used to evaluate AEs.

## 5 SELECTION AND WITHDRAWAL OF PARTICIPANTS

To be eligible for study participation, participants must meet all the inclusion criteria. Participants will be excluded from the study if they meet any exclusion criteria. No exceptions to these criteria will be granted by the sponsor.

The participant population to be enrolled in this study will consist of adult participants with histologically proven, relapsed or refractory, unresectable locally advanced or metastatic solid tumors.

### 5.1 Inclusion Criteria

1. Ability to provide informed consent and documentation of informed consent prior to initiation of any study-related tests or procedures that are not part of standard-of-care for the participant's disease. Participants must also be willing and able to comply with study procedures, including the acquisition of specified research specimens.
2. Age  $\geq$  18 years old.
3. Archival or formalin-fixed paraffin-embedded (FFPE) tissue must be available for determination of B7-H3 (Module A) and B7-H3 and PD-L1 expression (Module B). Participants may undergo a fresh tumor biopsy to obtain a specimen for testing if a tumor sample is not available; mCRPC with bone only disease not amenable to fresh biopsy may be eligible in consultation with the sponsor.
4. Eastern Cooperative Oncology Group (ECOG) performance status of  $\leq$  2.
5. Life expectancy  $\geq$  12 weeks for Dose Escalation Phase and  $\geq$  24 weeks for Cohort Expansion Phase.
6. Measurable disease as per RECIST v1.1 criteria ([Appendix 5](#)). Participants with mCRPC without measurable disease may be enrolled. Cutaneous or subcutaneous lesions must be measurable by calipers. Note: Lesions to be used as measurable disease for the purpose of response assessment must not reside in a field that has been subjected to prior radiotherapy.
7. Tumor Histology Types

#### **Dose Escalation Phase of the Study:**

- a. Participants with histologically proven, relapsed or refractory, unresectable locally advanced or metastatic solid tumors of any histology for whom no therapy with demonstrated clinical benefit is available.

#### **Cohort Expansion Module A:**

- a. mCRPC that has progressed during or following one prior line of chemotherapy for metastatic disease, and if approved and available, no more than two prior lines of an anti-hormonal agent (e.g., abiraterone, enzalutamide) with a PSA value of at least 2 ng/mL and meeting at least one of the following:
  - Progression in measurable disease (RECIST v1.1).

- Appearance of 2 or more new bone lesions according to Prostate Cancer Working Group 2 (PCWG2).
- Rising PSA defined as at least two sequential rises in PSA (PSA obtained  $\geq$  1 week apart) over a reference value (the last PSA [PSA  $\geq$  2 ng/mL] measured before the first rise in PSA) (as defined by the PCWG2).

b. NSCLC

- Metastatic NSCLC who have failed standard cytotoxic, targeted, and biologic or checkpoint inhibitor therapy. No more than two prior lines of cytotoxic chemotherapy.

c. TNBC

- Locally advanced or metastatic TNBC that has progressed during or following at least one systemic therapy. American Society of Clinical Oncology (ASCO) College of American Pathologists (CAP) guidelines should be followed for establishing the diagnosis of TNBC ([76](#)).

- SCCHN that has progressed during or following at least one systemic therapy for metastatic or recurrent unresectable disease. No more than 2 prior lines of cytotoxic chemotherapy are allowed.
- Melanoma that has progressed during or following at least one systemic treatment for unresectable locally advanced or metastatic disease. Patients who are intolerant of or refused standard therapy are eligible.

**Cohort Expansion Module B:**

Participants with histologically proven, unresectable, locally advanced or metastatic solid tumors for whom no therapy with demonstrated clinical benefit is available as described below.

- SCCHN that has progressed following treatment with platinum-based chemotherapy for metastatic or recurrent disease, or progression of disease within 6 months of completing prior platinum therapy used as part of neoadjuvant, concurrent chemoradiation, or adjuvant therapy.
  - Participants with upper esophageal or salivary gland tumors will not be considered as SCCHN.
  - Participants who refuse radical resection for recurrent disease are eligible.
- mCRPC that has progressed during or following one prior line of chemotherapy for metastatic disease, and if approved and available, no more than two prior lines of anti-hormonal agent (e.g., abiraterone, enzalutamide) with a PSA value of at least 2 ng/mL and meeting at least one of the following:

- Progression in measurable disease (RECIST v1.1).
- Appearance of 2 or more new bone lesions according to Prostate Cancer Working Group 2 (PCWG2).
- Rising PSA defined as at least two sequential rises in PSA (PSA obtained  $\geq$  1 week apart) over a reference value (the last PSA [PSA  $\geq$  2 ng/mL] measured before the first rise in PSA) (as defined by the PCWG2).

- c. Tumor type TBD at a later date; cancer will be required to have progressed or recurred despite prior standard therapy for that specific tumor.

8. Acceptable laboratory parameters as follows:
  - a. Platelet count  $\geq 100 \times 10^3/\mu\text{L}$  without transfusion within 28 days prior to the initiation of study drug,
  - b. Absolute neutrophil count  $\geq 1.5 \times 10^3/\mu\text{L}$  in the absence of any growth factor support within 21 days prior to the initiation of study drug,
  - c. ALT/AST  $\leq 3.0 \times \text{ULN}$ ; for participants with hepatic metastases, ALT and AST  $\leq 5 \times \text{ULN}$ ,
  - d. Total bilirubin  $\leq 1.5 \times \text{ULN}$ , except participants with Gilbert's syndrome, who may enroll if the conjugated bilirubin is within normal limits,
  - e. Creatinine  $< 2 \text{ mg/dL}$ , or a calculated creatinine clearance (based on the Cockcroft-Gault formula) or measured creatinine clearance  $> 50 \text{ mL/min}$ ,
  - f. Negative urine or serum pregnancy test for women of childbearing potential.
  - g. Albumin  $\geq 3.0 \text{ g/dL}$
  - h. Hemoglobin  $\geq 8.0 \text{ g/dL}$  without transfusion within 28 days prior to initiation of study drug.
9. Female participants of childbearing potential, defined as not surgically sterilized (hysterectomy, bilateral salpingectomy, and bilateral oophorectomy) and between menarche and 1-year post menopause, must have a negative serum pregnancy test performed within 72 hours prior to the initiation of study drug administration. Female participants should abstain from egg donation during the study.
10. Female participants of childbearing potential and male participants with partners who are females of childbearing potential must agree to use highly-effective methods of contraception according to **Section 8.1.3** from the time of consent through 27 weeks after discontinuation of study drug administration. Male participants should abstain from sperm donation during the study.
11. The female of childbearing potential is not pregnant or breastfeeding or male participant is not expecting to father children within the projected duration of the study, starting with screening visit through 27 weeks after the last dose of study drug.

12. Module B only: Previous Checkpoint Inhibitor Therapy: Participants who have previously received an immune checkpoint inhibitor (e.g., anti-PD-L1, anti-PD-1, anti-CTLA-4) prior to enrollment must have toxicities related to the checkpoint inhibitor resolved to  $\leq$  Grade 1 or baseline (prior to the checkpoint inhibitor) to be eligible for enrollment. Note that participants who experienced previous hypothyroidism toxicity on a checkpoint inhibitor are eligible to enter study regardless of Common Terminology Criteria for Adverse Events (CTCAE) grade resolution as long as the participant is well controlled on thyroid replacement hormones.

## 5.2 Exclusion Criteria

Participants who meet any of the following criteria will be excluded from the study.

1. Participants with history of prior central nervous system (CNS) metastasis must have been treated, must be asymptomatic, and must not have any of the following at the time of enrollment:
  - a. Concurrent treatment for the CNS disease (e.g., surgery, radiation, corticosteroids  $> 10$  mg prednisone/day or equivalent),
  - b. Progression after primary treatment of CNS metastases on imaging with MRI, CT or positron emission tomography (PET)/CT within 6 months prior to screening,
  - c. History of leptomeningeal disease or spinal cord compression.
2. Module B only: Participants with any history of known or suspected autoimmune disease with the specific exceptions of vitiligo, resolved childhood atopic dermatitis, psoriasis not requiring systemic treatment (within the past 2 years), and participants with a history of Grave's disease that are now euthyroid clinically and by laboratory testing.
3. Treatment with any investigational therapy within the 4 weeks prior to the initiation of study drug administration.
4. Module B only: Previous Checkpoint Inhibitor Therapy: Participants who experienced the following immune checkpoint inhibitor-related AEs make the participant ineligible, despite the AE resolving to  $\leq$  Grade 1 or baseline:
  - a.  $\geq$  Grade 3 ocular AE,
  - b. Changes in liver function tests that met the criteria for Hy's Law ( $> 3 \times$  ULN of either ALT/AST with concurrent  $> 2 \times$  ULN of total bilirubin and without alternate etiology),
  - c.  $\geq$  Grade 3 neurologic toxicity,
  - d.  $\geq$  Grade 3 colitis,
  - e.  $\geq$  Grade 3 pneumonitis,
  - f.  $\geq$  Grade 3 renal toxicity,

g.  $\geq$  Grade 3 skin toxicity.

5. Prior treatment with MGD009, enoblituzumab, or other B7-H3 targeted agents for cancer.
6. Treatment with any systemic anti-cancer therapy within the interval provided prior to study drug administration
  - a. 4 weeks for cytotoxic chemotherapy for all tumor types or anti-hormonal therapy (e.g., enzalutamide, abiraterone) for mCRPC,
  - b. 14 days or 5 half-lives, whichever is longer, for small molecule targeted or kinase inhibitors,
  - c. 4 weeks prior for biologic agents,
  - d. Prior radioligand (e.g., radium-223) within 6 months for mCRPC in the Cohort Expansion Phase.
7. Treatment with mediastinal or pelvic radiation therapy within 4 weeks prior to the initiation of study drug administration. Palliative, limited field radiation for symptom control to soft tissues, or bone lesions within 2 weeks prior to the initiation of study drug administration.
8. Module B only: Treatment with systemic corticosteroids ( $> 10$  mg per day prednisone or equivalent) or other immune suppressive drugs within the 14 days prior to the initiation of study drug administration.
9. Clinically significant cardiovascular disease including but not limited to:
  - a. Myocardial infarction or unstable angina within the 6 months prior to the initiation of study drug,
  - b. Stroke or transient ischemic attack within 6 months prior to the initiation of study drug,
  - c. Clinically significant cardiac arrhythmias, e.g., atrial fibrillation that are not well controlled with optimal medical intervention,
  - d. Uncontrolled hypertension: systolic blood pressure  $> 180$  mmHg, diastolic blood pressure  $> 100$  mmHg,
  - e. Congestive heart failure (New York Heart Association class I-IV),
  - f. Pericarditis or pericardial effusion,
  - g. Myocarditis,
  - h. Participants with a baseline left ventricular ejection fraction (LVEF) of  $< 50\%$ ,
  - i. Prolongation of QTcF  $> 480$  milliseconds.
10. Clinically significant pulmonary compromise, including pneumonia, pneumonitis, or a requirement for supplemental oxygen use to maintain adequate oxygenation or history of  $\geq$  Grade 3 drug-induced or radiation pneumonitis.

11. Evidence of active viral, bacterial, or systemic fungal infection requiring parenteral antibiotic, antiviral, or antifungal treatment within 7 days prior to the initiation of study drug. Participants requiring any systemic antiviral, antifungal, or antibacterial therapy for active infection must have completed treatment no less than one week prior to the initiation of study drug.
12. Known history of positive testing for human immunodeficiency virus or history of acquired immune deficiency syndrome.
13. Known history of hepatitis B or hepatitis C infection or known positive test for hepatitis B surface antigen, hepatitis B core antigen, or hepatitis C polymerase chain reaction.
14. History of prior allogeneic bone marrow, stem-cell, or solid organ transplantation.
15. Second primary invasive malignancy that has not been in remission for greater than 2 years except non-melanoma skin cancer; cervical carcinoma in situ on biopsy; or squamous intraepithelial lesion on Pap smear; localized prostate cancer (Gleason score < 6); or resected melanoma in situ.
16. Major trauma or major surgery within 4 weeks prior to the initiation of study drug administration.
17. Any serious underlying medical or psychiatric condition that would impair the ability of the participants to receive or tolerate the planned treatment at the study site.
18. Known hypersensitivity to recombinant proteins, or any excipient contained in the drug formulation or custom vehicle (**Section 6.5**).
19. Vaccination with any live virus vaccine within 4 weeks prior to the initiation of study drug administration. Inactivated annual influenza vaccination is allowed.
20. Dementia or altered mental status that would preclude understanding and rendering of informed consent.
21. Prisoners or other individuals who are involuntarily detained.
22. Any investigative site personnel directly affiliated with this study.
23. Any issue that, in the opinion of the investigator in consultation with the sponsor, would contraindicate the participant's participation in the study or confound the results of the study.
24. Clinically significant venous insufficiency.
25. > Grade 1 peripheral neuropathy.
26. Evidence of pleural effusion.
27. Evidence of ascites.
28. Serum testosterone >50 ng/dl or >1.7 nmol/L in mCRPC in Module A Cohort Expansion Phase and Module B Cohort Expansion Phase.

29. Confirmed or presumed COVID-19/SARS-CoV-2 infection. While SARS-CoV-2 testing is not mandatory for study entry, testing should follow local clinical practice guidelines/standards. Participants with a positive test result for SARS-CoV-2 infection, known asymptomatic infection, or presumed infection are excluded.

### **5.3 Withdrawal of Participant from the Study**

Participants who withdraw before Study Day 21 (Module A) or Study Day 42 (Module B) during the Dose Escalation Phase for a reason unrelated to drug toxicity may be considered to have inadequate data to support dose escalation. In this case, replacement participants may be enrolled in the same dose level. These participants will be followed for safety assessments (see [Section 12.2](#)).

A participant may be determined to be LTFU after there have been at least 3 documented phone or electronic contact attempts. If this fails, a certified letter should be sent to the participant. Only after these attempts have failed can a participant be determined to be LTFU.

### **5.4 Rules for Study Treatment Discontinuation**

Participants who tolerate treatment may continue to receive treatment with the study drug(s) as specified in the protocol until any one of the following conditions are met:

- Participant meets RECIST v1.1 criteria for disease progression
- Participant meets PCWG-2 criteria for radiographic progression
- Withdrawal of participant due to an AE or SAE
- Withdrawal of participant consent
- Completion of protocol-defined therapy
- Investigator discretion
- Pregnancy
- Occurrence of drug-related DLT or AEs that lead to discontinuation of study drug
- Dose delay > 21 days due to AEs unless approved by the sponsor.
- The sponsor, investigator, or regulatory agency terminates the study
- Death

For individual participants who meet these criteria, but who are otherwise considered to be experiencing clinical benefit in the judgment of the investigator, consideration may be given to continue therapy of MGC018 alone (Module A) or in combination with MGA012 (Module B), for up to maximum of total of 18 cycles (i.e. approximately 2 years), on a case-by-case basis in consultation with the sponsor. If the investigator decides that the participant should be withdrawn from the study or from dosing for any reason other than

disease progression, the sponsor or its designee must be alerted within 24 hours by completing the appropriate electronic case report forms (eCRFs) ([Section 12.2.2](#)).

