MGC018 has an average drug-to-antibody ratio (DAR) of ~ 2.7, and an average molecular weight of ~ 150 kDa. MGC018 is designed to bind to cell-surface B7-H3, internalize into cells, and release the cytotoxic duocarmycin drug. Following binding to cell-surface B7-H3 and internalization of MGC018 through endocytosis, the peptide linker is cleaved by lysosomal proteases, such as cathepsin B. Subsequently, 2 self-elimination reactions occur on the duocarmycin moiety to generate *seco*-DUBA (SYD978), which then spontaneously rearranges to form the activated duocarmycin drug (also known as DUBA or SYD986), which can then bind and alkylate DNA ([Figure 1](#)). The irreversible alkylation of DNA disrupts the nucleic acid architecture, ultimately leading to cell death. Due to the nature of the “cleavable” linker/payload, the protease-cleaved, activated DUBA is membrane permeable and, when released by dying cells, can cause bystander killing of neighboring tumor cells, irrespective of B7-H3 expression (70) ([Figure 2](#)). Importantly, the bystander killing property of the vc-*seco*-DUBA linker/payload may afford MGC018 therapeutic benefit toward heterogeneous B7-H3-expressing tumors.

[figure not shown]

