### 2.3.1.1.2 MGC018 Pharmacokinetics and Toxicology

A summary of nonclinical pharmacokinetic (PK) and toxicology data with MGC018 are provided below; please reference the **MGC018 Investigator Brochure** for a more detailed description.

The nonclinical toxicology program for MGC018 was performed exclusively in the cynomolgus monkey as MGC018 does not bind to B7-H3 in mouse or rat. The cynomolgus monkey was selected as the most appropriate animal model for nonclinical safety evaluation of MGC018 given the homology of cynomolgus monkey and human B7-H3, the ability of MGC018 to bind with nearly identical affinity to human and cynomolgus monkey B7-H3, and the concordance of staining pattern for MGC018 toward panels of normal human and cynomolgus monkey tissues.

A GLP tissue cross-reactivity study, performed on a panel of normal human tissues, demonstrated that MGC018 staining the membrane and cytoplasm of mononuclear cells found in human lymphoid tissues (spleen, thymus, and tonsil), as well as rare or very rare cases of stomach or heart, respectively. Membrane and cytoplasm staining was observed in a few epithelial cell types: hepatocyte epithelium in liver (2 of 3 samples with weak intensity and occasional staining at the higher of 2 validated MGC018-biotinylated (MGC018-Bio) antibody concentrations); the epidermis and hair follicle epithelium in skin (2 of 3 samples with weak to moderate intensity and rare to occasional staining at both the high and low MGC018-Bio antibody concentrations); and extravillous trophoblasts and amniotic epithelium in the placenta. All staining in this study represented expected reactivity, and no unanticipated cross-reactivity of MGC018 was observed (41, 52, 55, 59, 64, 81, 82).

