## 7.7 Nervous System Toxicity

Consider discontinuation of **MGA012** for patients who experience Grade 2 myasthenia gravis, Grade 2 Guillain-Barre syndrome, and permanently discontinue study drugs for any grade transverse myelitis. Management guidelines for participants experiencing nervous system toxicity are as follows:

- Grade 1 - No specific therapy required; close monitoring of neuropathy.
- Grade 2 - Hold study drugs.
  - Consider neurology consultation.
  - Consider corticosteroids: 1 to 2 mg/kg of oral prednisone or equivalent per day divided twice daily. Taper corticosteroids over 4 weeks or as clinically indicated.
  - Resume study drug administration at next scheduled dose if:
    - Resolves to  $\leq$  Grade 1 within 21 days with or without treatment
- Grade 3 and 4 - Permanently discontinue study drugs.
  - Consider hospitalization and neurology consultation
  - Begin corticosteroids: 2 to 4 mg/kg of oral or IV methylprednisolone or equivalent per day divided twice daily. Continue IV methylprednisolone 2 mg/kg/day for a total of 5 days then switch to oral prednisolone 1 mg/kg/day  $\times$  3 days, then reduce to 60 mg/day prednisolone. Reduce prednisolone dose by 10 mg every 7 days (as toxicity allows) until dose is 10 mg/day. Once steroid dose is 10 mg/day, reduce by 5 mg every 7 days then stop.

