## 9.8 Clinical Laboratory Tests

Blood and urine samples will be collected at the times specified in [Appendix 1](#). Hematology, chemistry, pregnancy, urinalysis, coagulation time, and endocrine evaluation tests (as applicable) will be performed locally. Test results for pregnancy, chemistry, and hematology must be reviewed prior to all infusions of MGC018. On the dosing days, clinical laboratory tests should be collected prior to administration of prophylactic pre-medications. Local laboratory tests to be performed are presented in [Appendix 2](#).

- A blood sample for local testing of the tumor marker PSA will be collected from participants with mCRPC. PSA measurements are performed at the times specified in [Appendix 1](#) and approximately every 12 weeks during the post-treatment follow-up period until disease progression, start of another cancer therapy, or the study cutoff date, whichever comes first.
- A blood sample for testosterone will be collected from participants with mCRPC in Cohort Expansion. Testosterone measurements are performed at the times specified in [Appendix 1](#) and approximately every 12 weeks during the post-treatment follow-up period until disease progression, start of another cancer therapy, or the study cutoff date, whichever comes first.

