## 12.2.5 Pregnancy

All reports of pregnancy in female participants or partners of male participants must be reported to the sponsor by study-site personnel within 24 hours of their knowledge of the event using the Pregnancy Exposure Form. Abnormal pregnancy outcomes (e.g., spontaneous abortion, fetal death, stillbirth, congenital anomalies, ectopic pregnancy) are considered SAEs and must be reported using the SAE Report form. Any participant who becomes pregnant during the study must discontinue further study drug administration.

Because the effect of the study drug on sperm is unknown, pregnancies in partners of male participants included in the study will be reported by the study-site personnel within 24 hours of their knowledge of the event. If the female partner of a male participant becomes pregnant, the partner must be requested to complete a Pregnant Partner Consent Form so that pregnant partner, fetal, and/or newborn information can be collected.

Upon confirmation of serum or urine pregnancy testing, the participant will be followed for the outcome of pregnancy. Follow-up information will be collected for all live newborns at

birth and 6 months after the birth. All necessary information will be collected to assess the effects of study drug on the newborn. If necessary, the follow-up period will be extended for the newborn.

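### The clinical-benefit exception in Protocol Section 5.4 excludes no stopping criterion, so as written it reaches pregnancy, where Section 12.2.5 requires study drug to stop

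*Protocol*

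**What the plan says.** Protocol Section 5.4 says treatment may continue until any one of 11 listed conditions occurs. In order, they are RECIST progression, PCWG-2 radiographic progression, withdrawal for an adverse event, withdrawal of consent, completed therapy, investigator discretion, pregnancy, a drug-related DLT or adverse event, a dose delay beyond 21 days unless the sponsor approves, study termination, and death.

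The next paragraph begins "For individual participants who meet these criteria, but who are otherwise considered to be experiencing clinical benefit in the judgment of the investigator". For these participants it allows continued MGC018, alone or with MGA012, to be considered for up to 18 cycles in total. The decision is individual, and the sponsor must be consulted. The sentence names no condition as outside its scope.

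Section 12.2.5 deals with pregnancy directly: "Any participant who becomes pregnant during the study must discontinue further study drug administration". It states no exception.

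Section 9.8 adds a check before dosing: "Test results for pregnancy, chemistry, and hematology must be reviewed prior to all infusions of MGC018". It does not say what follows a positive test; that is left to Section 12.2.5.

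**The concern.** Two sections give different answers to the same question. Section 5.4 makes further dosing of a pregnant participant something that may be considered if the investigator sees benefit, while Section 12.2.5 rules it out. Sites are sent to Section 5.4 for discontinuation criteria by other parts of the protocol (Sections 4.2, 4.4 and 9.16). Section 5.4 itself cross-refers to Section 12.2.2 for reporting but not to Section 12.2.5.

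The stake is fetal and participant safety. On the payload, Section 2.1 says: "The irreversible alkylation of DNA disrupts the nucleic acid architecture, ultimately leading to cell death". In the human tissue cross-reactivity study (Section 2.3.1.1.2), membrane and cytoplasmic staining included some epithelial cell types "and extravillous trophoblasts and amniotic epithelium in the placenta". Section 2.1 describes the reactivity in that study as generally weak or weak to moderate in intensity and rare to occasional in frequency. This is evidence of binding, not of harm. The sponsor's own caution shows in inclusion criterion 10 of Section 5.1, which requires contraception "from the time of consent through 27 weeks after discontinuation of study drug administration".

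**Working it through.** No calculation of power or error rate applies. The check is a reading of the sections against one another.

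**Step 1: what the exception covers on its wording.** Section 5.4 has 11 conditions and the exception excludes 0 of them. Pregnancy is the seventh.

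**Step 2: what it could cover in practice.** Some conditions cannot be overridden whatever the wording:
- Four by their nature: withdrawn consent, completed therapy (the exception keeps the 18-cycle limit), study termination and death.
- Two that are met only once stopping has been decided: withdrawal for an adverse event, and investigator discretion.

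That leaves 11 − 4 − 2 = 5: the two progression conditions, the delay beyond 21 days, the DLT/adverse-event condition, and pregnancy. If the DLT/adverse-event condition is also met only once stopping has been decided, 5 − 1 = 4 remain. Pregnancy is among them on either count, because it is a state in which dosing could physically go on and benefit could be claimed.

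**Step 3: is each remaining condition consistent with the rest of the protocol?**

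| Condition within reach | Rule elsewhere | Result |
|---|---|---|
| RECIST or PCWG-2 progression | Treatment beyond progression is an understandable use of such a clause | No conflict |
| Delay beyond 21 days | The condition has its own sponsor approval; Section 4.4.2 allows continuation for clinical benefit | No conflict |
| DLT/adverse event (one reading only) | Sections 4.4 and 4.4.2 send toxicity restarts to Section 7 | Not shown to conflict; see objection |
| Pregnancy | Section 12.2.5: must stop, no exception | Conflict as written |

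**Step 4: does other text settle it?**
- Section 4.1 makes further cycles conditional on not meeting the criteria for permanent discontinuation. The Section 5.4 exception is written for people who do meet the criteria, so Section 4.1 does not close the gap.
- Section 9.8 governs review of the test result, not the decision that follows.
- No sentence ranks Section 12.2.5 above Section 5.4.

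**The case against.** The case against is substantial. Section 5.4 authorises no dosing; it allows a discussion with the sponsor. Section 12.2.5 then fixes the outcome, so a site can obey both, and a specific mandatory rule ordinarily prevails over a general permissive one. Pregnancy must also be reported within 24 hours (Sections 12.2.2 and 12.2.5), so the sponsor would know. Finally, the exception reads naturally as a treat-beyond-progression clause, and since six or seven of the 11 conditions cannot be overridden anyway, the reference to the criteria was probably never meant to take in the whole list.

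Most of this stands, and it limits the practical risk. It does not remove the inconsistency. The sentence is not confined to progression, and pregnancy is one of the few conditions it can actually reach. A safeguard that works only if the reader infers the drafters' intent is better written down.

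A reader might also infer that the exception reopens the permanent toxicity stops in Section 7, through the condition "Occurrence of drug-related DLT or AEs that lead to discontinuation of study drug". The documents do not support that as a second conflict. The inference depends on whether the closing phrase qualifies DLTs as well as adverse events; if it does, the condition is met only after stopping has been decided. Section 7.7 is firm on its own terms ("permanently discontinue study drugs for any grade transverse myelitis"), and Sections 4.4 and 4.4.2 route toxicity restarts to Section 7. Section 7.2, for its part, describes its principles as open to local adaptation.

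**Conclusion.** The point holds for pregnancy alone. One of the 11 conditions in Section 5.4 falls within the exception's wording and conflicts with mandatory text elsewhere. It is a minor safety inconsistency.

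This rests on two readings: that the exception applies to every listed condition it does not exclude, and that no other provision gives Section 12.2.5 priority. I found none.

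It would be wrong to infer that the protocol permits dosing in pregnancy. Section 12.2.5 is unconditional, and Section 5.4 goes no further than consideration with the sponsor. Nor can the number of participants at risk be estimated, since the documents do not say how many women of childbearing potential will enrol.

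**What to change.** Add one sentence after the exception in Section 5.4:

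*This exception does not apply to pregnancy; any participant who becomes pregnant must discontinue study drug (Section 12.2.5).*

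Leave the DLT/adverse-event condition unchanged. Tying it to events for which Section 4.4 or Section 7 requires stopping would drop most DLTs that Section 7 does not cover, because Section 4.4 and Table 6 mostly ask the investigator to consider stopping. Leave the condition on delays beyond 21 days unchanged too, as it already carries its own sponsor approval.

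The cost is one sentence at the next amendment, with no change to sample size, data collection or analyses.
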